7.5 Follow-Up Procedures and Therapy Transitions

Adverse events identified in the study will be followed to resolution. No additional follow-up procedures or therapy transitions are required.

7.6 Study Timetable / Schedule of Events

Table 2. Schedule of Events

Assessment	Visit 1			Visit 2
	Screening	Treatment	Post-Treatment	Follow-up
Demographics	X			
Medical History	X			
Physical Exam (Height & Weight)	X			
Inclusion/Exclusion Criteria	X			
Informed Consent	X			
Randomization	X			
Concomitant Medications	X		X	
Procedure Completion		X		
Discomfort Assessment			X	
Provider Satisfaction Assessment			X	
PDPH				X
Adverse Event Assessment			X	X
Adverse Device Effect Assessment			X	X

7.7 Deviations from the Clinical Protocol

The study will be conducted as described in this protocol. Investigators are not permitted to deviate from this protocol except to protect patient rights, safety, or well-being. Any deviations from this protocol must be documented by the Investigator. A description of the deviation from the protocol and justification must be recorded on the Protocol Deviation Form. If an emergency situation arises in which the rights, safety or well-being of a subject may require immediate alternative intervention, the Investigator should act in the best interest of the subject. Sponsor and the site's IRB must be notified immediately if this occurs. This should be followed with written confirmation that describes the emergency action and outcomes, to Sponsor and per IRB reporting requirements.

Protocol deviations will be reviewed during routine monitoring visits. Investigators will be required to identify preventive and corrective actions to prevent further deviations. An Investigator may be disqualified from the study for repeated and/or egregious protocol deviations.

7.8 Subject Withdrawal

Subject withdrawals are not anticipated due to the short nature of the subject participation in the study. If a subject withdraws, a Study Exit CRF will be completed.

7.9 Subject Compensation

Subjects will receive no payment or stipend for participation in this study.

8 Data Collection and Analysis

8.1 Subject Population(s) for Analysis

The study populations are defined as follows:

- Intent-to-treat population (ITT): Consists of all randomized subjects according to their randomized group.
- Per-protocol population (PP): Consists of all subjects who received their randomized treatment, did not have an inclusion or exclusion violation, had a procedure success, and did not have a major protocol deviation.

The primary analysis and all study results will be analyzed using the ITT population. The primary analysis will be repeated using the PP population.

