6.3.2 Secondary Clinical Endpoint(s)

1. Incidence of first-insertion success (a case that does not require any reinsertions, but can include any number of redirections)
2. Number of redirections (any forward movement of the needle in a new direction not preceded by withdrawal from the skin, counted until confirmation of spinal canal access can be assessed)
3. Number of passes (any forward movement of the needle, calculated as the sum of insertions and redirections)
4. Incidence of first-pass success (a case that does not require reinsertions or redirections)
5. Subject discomfort during landmarking on a 100mm VAS (See Section 17.1)

6. Provider confidence with the identified insertion site on a 1-5 Likert scale (See Section 17.2)
7. Procedure success as confirmed by the following procedure-specific methods:
 - Epidural anesthesia: able to achieve a T10 or greater bilateral sensory level change to cold
 - Spinal anesthesia: able to achieve sensory blockade to surgical stimulus at level desired
 - Diagnostic and therapeutic LP: return of CSF
 - Blood patch: able to inject homologous blood into epidural space (entry confirmed by loss-of-resistance)

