Additional Hypothesis 5: The null hypothesis that the mean subject discomfort rated during landmarking from 0 to 10 is higher in the VerTouch subjects compared to the control group using a T-test with unequal variance assumption ($H_0: \mu_1 \geq \mu_2$ vs $H_1: \mu_1 < \mu_2$ where μ_1 is the mean in VerTouch subjects and μ_2 is the mean in control subjects). The results will be considered statistically significant if the one-sided p-value is less than 0.025.

Additional Hypothesis 6: The null hypothesis that the mean provider confidence with the identified insertion site rated 1 to 5 is lower in the VerTouch subjects compared to the control group using a T-test with unequal variance assumption ($H_0: \mu_1 \leq \mu_2$ vs $H_1: \mu_1 > \mu_2$ where μ_1 is the mean in VerTouch subjects and μ_2 is the mean in control subjects). The results will be considered statistically significant if the one-sided p-value is less than 0.025.

Additional Hypothesis 7: The null hypothesis that the binary rate of procedure success is the same in both groups will be analyzed using a likelihood ratio test ($H_0: p_1 = p_2$ vs $H_1: p_1 \neq p_2$ where p_1 is the success rate in VerTouch subjects and p_2 is the success rate in control subjects). The results will be considered statistically significant if the two-sided p-value is less than 0.05 and the VerTouch success rate is higher than the control rate).

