8.2.2 Primary Effectiveness Analysis

The study is designed to evaluate whether the use of the VerTouch device is able to reduce the number of insertion attempts to successfully access the spinal canal in a spinal puncture as compared to the conventional palpation technique. The primary hypothesis test will be performed by a bootstrap analysis resampling the cases in each group. The null hypothesis for the analysis is:

$$H_0: \mu_1 \geq \mu_2 \text{ vs } H_1: \mu_1 < \mu_2$$

Where μ_1 is the mean attempts in the VerTouch group and μ_2 is the mean for palpation.

This hypothesis will be evaluated using a bootstrap analysis with a one-sided 0.025 test to indicate statistical significance. The results will be presented for the difference in means and the associated 95% CI; and the ratio of the VerTouch mean divided by the palpation mean and the associated 95% CI.

The primary analysis will include the total insertions for each subject regardless of success on the final placement attempt.

The following supporting analyses will be performed:

- The primary analysis will be performed only for subjects who had a procedure success.
- If there are missing data, best- and worst-case imputation analyses will be performed. For the worst-case imputation, the highest observed value will be imputed in the VerTouch group and the lowest value in the palpation group. The best-case analysis reverses the pattern of imputations.
- A Wilcoxon rank-sum test will be used to evaluate the null hypothesis that median attempts are the same in both arms using a two-sided test with a p-value less than or equal to 0.05 considered significant.
- Homogeneity of the log-transformed count results will be assessed using an ANOVA with site, treatment, and site-treatment interaction terms. A p-value for the site-treatment interaction of less than or equal to 0.15 will be considered statistically significant for this analysis. The n, mean, and SD of values by study site will be provided by treatment group.
- The observed attempts will be evaluated through a t-test for unequal variances comparing the difference in the log (insertion attempts) for each group. The difference will be transformed with the exponent function to provide the ratio of the geometric mean attempts and a two-sided 95% CI for the ratio.

The following subgroups will be considered in exploratory covariate analyses:

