8.3.3.3 Sensitivity and Supporting Analyses

Several supporting analyses are planned for this study:

- The primary analysis will be performed only for subjects who had a procedure success.
- If there are missing data, best- and worst-case imputation analyses will be performed. For the worst-case imputation, the highest observed value will be imputed in the VerTouch group and the lowest value in the palpation group. The best-case analysis reverses the pattern of imputations.
- A Wilcoxon rank-sum test will be used to evaluate the null hypothesis that median attempts are the same in both arms using a two-sided test with a p-value less than or equal to 0.05 considered significant.
- Homogeneity of the study results will be assessed using an ANOVA with site, treatment, and site-treatment interaction terms. A p-value for the site-treatment interaction of less than or equal to 0.15 will be considered statistically significant for this analysis. The n, mean, and SD of values by study site will be provided by treatment group.
- The observed attempts will be evaluated through a t-test for unequal variances comparing the difference in the log (insertion attempts) for each group. The difference will be transformed with the exponent function to provide the ratio of the geometric mean attempts and a two-sided 95% CI for the ratio.

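### The per-protocol set requires procedure success, so the per-protocol repeat of the primary analysis conditions on a treatment outcome rather than on adherence

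*Protocol*

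**What the plan says.** Protocol 8.1 makes ITT the main population: "The primary analysis and all study results will be analyzed using the ITT population". It adds that "The primary analysis will be repeated using the PP population". Membership of the per-protocol set needs four things: the randomised treatment was received, there was no eligibility violation, and the subject "had a procedure success, and did not have a major protocol deviation". SAP 7 gives the same definition and the same use.

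Protocol 6.3.2 lists procedure success as secondary endpoint 7 ("Procedure success as confirmed by the following procedure-specific methods"). The methods are return of CSF, a sensory level or block, or injection into the epidural space, depending on the procedure. Protocol 8.2.1 tests it as Additional Hypothesis 7: "The null hypothesis that the binary rate of procedure success is the same in both groups".

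For the primary analysis, Protocol 8.2.2 says: "The primary analysis will include the total insertions for each subject regardless of success on the final placement attempt". Protocol 8.2.2 and SAP 8.3.3.3 then list a separate supporting analysis: "The primary analysis will be performed only for subjects who had a procedure success".

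**The concern.** A per-protocol analysis is normally meant to show whether the result holds among subjects treated as planned. Three of the four criteria serve that purpose. The fourth does not: a provider can follow every step and still fail, and failure may itself be a consequence of the assigned technique.

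Selecting on success breaks the randomised comparison. If failed cases tend to carry more insertions, dropping them lowers the mean of whichever arm fails more often. The per-protocol result could then agree or disagree with the ITT result for reasons unrelated to adherence.

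There is also a gap in coverage. Every per-protocol subject is a procedure success, so the per-protocol set sits inside the success-only set. The two supporting analyses share one selection, and neither isolates adherence with the failures kept in.

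**Working it through.** **1. The plan's own figure.** The documents attach no number to the per-protocol set. The stated power that can be checked is 90% for first-attempt success, 50% against 81%, with 48 per group (Protocol 6.4.1). With pooled p = 0.655 and two-sided 0.05:

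z = [0.31 × √48 − 1.96 × √(2 × 0.655 × 0.345)] / √(0.81 × 0.19 + 0.50 × 0.50) = (2.148 − 1.318) / 0.636 = 1.31, so power is 0.904.

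It reproduces, and the per-protocol definition does not enter it.

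**2. Where bias comes from.** In one arm, let f be the share of failures, and let m_F and m_S be the mean insertions in failures and successes. The mean over all subjects is M = (1 − f)m_S + f·m_F, so M − m_S = f·g with g = m_F − m_S. For the difference VerTouch minus palpation:

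(difference in successes) − (difference in all subjects) = f_P·g_P − f_T·g_T

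This is zero when f and g are the same in both arms. It favours VerTouch when f_T·g_T is the larger and palpation when f_P·g_P is the larger. If failed cases have low counts (g negative), the sign reverses. The formula leaves aside the other three per-protocol criteria.

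**3. Size, under assumptions.** From the documents: 48 per group; palpation mean 2.1 and SD 1.5, with about 50% first-attempt success (Protocol 6.4.1); and the test, "This hypothesis will be evaluated using a bootstrap analysis with a one-sided 0.025 test to indicate statistical significance". The only failure rate given is 6.3%, a literature figure for inadequate analgesic effect in neuraxial anesthesia (Protocol 9.3), not split by arm. All other failure rates below are assumed, as is the rule that failures occur only in subjects with 3 or more insertions.

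Counts were the ceiling of the absolute value of a normal mixture (weight 0.6 on mean 0, SD 1.0; weight 0.4 on mean 2.5, SD 2). This gives mean 2.11, SD 1.48 and 48% with one insertion. Both arms had this distribution, so there was no true effect. There were 3,000 simulated trials per scenario, with Monte Carlo SE about 0.003 near 0.025.

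| Failing, VerTouch / palpation | Mean difference, failures excluded | Type I error, failures kept | Type I error, failures excluded |
|---|---|---|---|
| 6.3% / 6.3% | 0.00 | 0.024 | 0.028 |
| 10% / 5% | -0.12 | 0.027 | 0.070 |
| 15% / 5% | -0.25 | 0.031 | 0.166 |
| 5% / 15% | +0.26 | 0.028 | 0.002 |

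With 48 per group, 10% against 5% means 4.8 against 2.4 failures.

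**4. Hand check of the second row.** In that mixture, subjects with 3 or more insertions average 4.17. The success-only means are (2.11 − 0.10 × 4.17) / 0.90 = 1.88 and (2.11 − 0.05 × 4.17) / 0.95 = 2.00. The difference is -0.12, as simulated.

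**5. With a true benefit.** VerTouch counts were drawn with mean 1.18, SD 0.60 and 90% at one insertion. The difference over all subjects was -0.92. Excluding failures gave -0.93 with 5% failing in each arm, -0.83 with 2% VerTouch against 6.3% palpation, and -0.60 with 2% against 15%. If the device also fails less often, this selection understates its benefit.

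**The case against.** **Nothing decisive rests on this set.** The primary test is ITT and counts failed cases, and the testing sequence in Protocol 8.2.1 never refers to the per-protocol set. This stands, and it limits the point to a supporting result.

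**Unequal failure would be visible.** Procedure success is compared between arms, and SAP 8.3.1 reports ITT and per-protocol numbers by group. This stands in part: a reader could see the imbalance, but would still have no adherence analysis free of it.

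**The criterion may be an evaluability rule.** The stated aim is to reduce attempts needed for successful access, so a count from a case without access is arguably incomplete. That is a fair reading. It does not rescue the definition, because the primary analysis counts those cases deliberately and the separate success-only analysis already addresses that question.

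**Failures need not have many attempts.** A block can be inadequate after one clean insertion, and a referral to radiology may cut a count short. This stands, and it is one reason the direction is unknown.

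**The sets are not identical.** The per-protocol set also drops treatment crossovers, eligibility violations and major deviations. Correct: it is a subset of the success-only set, not a copy.

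**Conclusion.** The point holds for the per-protocol repeat only. Its definition conditions on a post-randomisation outcome, and the plan has no adherence check that keeps failed procedures. The ITT test, its alpha, its power and the testing sequence are unaffected.

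Any size is an assumption. In the no-effect scenarios above, the spurious difference ran from -0.25 to +0.26 insertions and was about zero with equal failure. These values rest on the assumed rates, the fitted count distribution and the rule placing failures at 3 or more insertions.

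Three stronger readings are tempting but not supported:

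- A reader might infer that the definition flatters VerTouch. The documents give no failure rate by arm, and the bias can favour either arm.
- A reader might infer that the per-protocol result can never support the ITT result. If failures are equally frequent and equally related to attempts in both arms, the bias is near zero.
- A reader might size the bias by placing all failures in the VerTouch arm and taking 1.1 as the mean of its successes. Protocol 6.4.1 reports 1.1 for the whole sample of 81, and nothing suggests that palpation never fails.

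**What to change.** Delete the procedure-success requirement from the per-protocol definition in Protocol 8.1 and SAP 7, leaving treatment received, eligibility and no major deviation. Keep the success-only supporting analysis in Protocol 8.2.2 and SAP 8.3.3.3, label it as conditional on a post-randomisation outcome, and show the number of failures by arm beside it.

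The cost is one phrase in two documents plus a label. No extra data or subjects are needed. If the study has started, Protocol 13.3 requires a documented amendment with IRB approval before the change is implemented.

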8.2 Statistical Methods

This section describes the planned statistical analyses for this study. A detailed Statistical Analysis Plan (SAP) will be completed and placed on file prior to enrollment. The SAP will contain a comprehensive explanation of the methodology used in the statistical analyses described below.

All CRF data will be made available in data listings or in Excel spreadsheets. Data listings will be sorted by subject and visit date, or adverse event onset date. All statistical analyses will be based on the available data. The study results will be reported in summary tables using standard descriptive statistics. Standard numeric descriptive statistics include the n (number of non-missing observations), mean, median, minimum value, and maximum value. Categorical data will be summarized using the counts and percentages based on the non-missing values.

Statistical analyses will be performed to assess the homogeneity of the study populations, evaluate the primary hypothesis, and evaluate the impact of covariates on the performance of the VerTouch device. Standard statistical tests used for

hypothesis testing are the t-test for numeric measures and the likelihood ratio chi-square test for categorical variables. For categorical variables with small cell counts (less than 5), Fisher's exact test will be used. For inferential analyses, unless otherwise indicated, a two-sided p-value of less than or equal to 0.05 will be considered statistically significant. All confidence intervals (CIs) will be two-sided 95% intervals. Note that p-values reported for tertiary and exploratory endpoints will be used for reporting but would not be used in product labeling.

8.2.1 Adjustments for Multiplicity

The study has a single primary endpoint needed for the superiority analysis. If that analysis reaches statistical significance, then the following additional hypothesis of the secondary variables will be considered sequentially such that if one analysis is statistically significant, then the next hypothesis can be evaluated to control for the Type I error for these analyses:

Additional Hypothesis 1: The null hypothesis that the binary rate of first-attempt success is the same in both groups will be analyzed using a likelihood ratio test ($H_0: p_1 = p_2$ vs $H_1: p_1 \neq p_2$ where p_1 is the success rate in VerTouch subjects and p_2 is the success rate in control subjects). The results will be considered statistically significant if the two-sided p-value is less than 0.05 and the VerTouch success rate is higher than the control rate).

Additional Hypothesis 2: The null hypothesis that the mean number of redirections is the higher in the VerTouch subjects compared to the control group using a T-test with unequal variance assumption ($H_0: \mu_1 \geq \mu_2$ vs $H_1: \mu_1 < \mu_2$ where μ_1 is the mean in VerTouch subjects and μ_2 is the mean in control subjects). The results will be considered statistically significant if the one-sided p-value is less than 0.025.

Additional Hypothesis 3: The null hypothesis that the mean number of passes is the higher in the VerTouch subjects compared to the control group using a T-test with unequal variance assumption ($H_0: \mu_1 \geq \mu_2$ vs $H_1: \mu_1 < \mu_2$ where μ_1 is the mean in VerTouch subjects and μ_2 is the mean in control subjects). The results will be considered statistically significant if the one-sided p-value is less than 0.025.

Additional Hypothesis 4: The null hypothesis that the binary rate of first-pass success is the same in both groups will be analyzed using a likelihood ratio test ($H_0: p_1 = p_2$ vs $H_1: p_1 \neq p_2$ where p_1 is the success rate in VerTouch subjects and p_2 is the success rate in control subjects). The results will be

considered statistically significant if the two-sided p-value is less than 0.05 and the VerTouch success rate is higher than the control rate).

Additional Hypothesis 5: The null hypothesis that the mean subject discomfort rated during landmarking from 0 to 10 is higher in the VerTouch subjects compared to the control group using a T-test with unequal variance assumption ($H_0: \mu_1 \geq \mu_2$ vs $H_1: \mu_1 < \mu_2$ where μ_1 is the mean in VerTouch subjects and μ_2 is the mean in control subjects). The results will be considered statistically significant if the one-sided p-value is less than 0.025.

Additional Hypothesis 6: The null hypothesis that the mean provider confidence with the identified insertion site rated 1 to 5 is lower in the VerTouch subjects compared to the control group using a T-test with unequal variance assumption ($H_0: \mu_1 \leq \mu_2$ vs $H_1: \mu_1 > \mu_2$ where μ_1 is the mean in VerTouch subjects and μ_2 is the mean in control subjects). The results will be considered statistically significant if the one-sided p-value is less than 0.025.

Additional Hypothesis 7: The null hypothesis that the binary rate of procedure success is the same in both groups will be analyzed using a likelihood ratio test ($H_0: p_1 = p_2$ vs $H_1: p_1 \neq p_2$ where p_1 is the success rate in VerTouch subjects and p_2 is the success rate in control subjects). The results will be considered statistically significant if the two-sided p-value is less than 0.05 and the VerTouch success rate is higher than the control rate).

8.2.2 Primary Effectiveness Analysis

The study is designed to evaluate whether the use of the VerTouch device is able to reduce the number of insertion attempts to successfully access the spinal canal in a spinal puncture as compared to the conventional palpation technique. The primary hypothesis test will be performed by a bootstrap analysis resampling the cases in each group. The null hypothesis for the analysis is:

$$H_0: \mu_1 \geq \mu_2 \text{ vs } H_1: \mu_1 < \mu_2$$

Where μ_1 is the mean attempts in the VerTouch group and μ_2 is the mean for palpation.

This hypothesis will be evaluated using a bootstrap analysis with a one-sided 0.025 test to indicate statistical significance. The results will be presented for the difference in means and the associated 95% CI; and the ratio of the VerTouch mean divided by the palpation mean and the associated 95% CI.

The primary analysis will include the total insertions for each subject regardless of success on the final placement attempt.

The following supporting analyses will be performed:

- The primary analysis will be performed only for subjects who had a procedure success.
- If there are missing data, best- and worst-case imputation analyses will be performed. For the worst-case imputation, the highest observed value will be imputed in the VerTouch group and the lowest value in the palpation group. The best-case analysis reverses the pattern of imputations.
- A Wilcoxon rank-sum test will be used to evaluate the null hypothesis that median attempts are the same in both arms using a two-sided test with a p-value less than or equal to 0.05 considered significant.
- Homogeneity of the log-transformed count results will be assessed using an ANOVA with site, treatment, and site-treatment interaction terms. A p-value for the site-treatment interaction of less than or equal to 0.15 will be considered statistically significant for this analysis. The n, mean, and SD of values by study site will be provided by treatment group.
- The observed attempts will be evaluated through a t-test for unequal variances comparing the difference in the log (insertion attempts) for each group. The difference will be transformed with the exponent function to provide the ratio of the geometric mean attempts and a two-sided 95% CI for the ratio.

The following subgroups will be considered in exploratory covariate analyses:

- BMI (kg/m^2): underweight (<18.5), normal (18.5-24.9), overweight (25-29.9), class 1 obesity (30.0-34.9), class 2-3 obesity (≥ 35.0)
- Age (years): adolescent (<22), young adult (22-40), middle-aged adult (41-65), older adult (>65)
- Provider type: MD, PA, CRNA, AA, NP
- Provider specialty: emergency medicine, neurology, anesthesiology
- MD level (MDs only): resident, fellow, attending
- Provider years in practice: <5 , 5-10, >10
- Provider experience (number of neuraxial procedures in past 12 months): 5-25, 26-50, 51-100, >100

- Neuraxial procedure: diagnostic LP, therapeutic LP, neuraxial anesthesia, blood patch
- Medication given for procedure: none, pain, anti-anxiety
- Needle type: spinal 20-22G cutting, spinal 20-22G non-cutting, spinal >22G, Tuohy, CSE
- VerTouch workflow (VerTouch subjects only): marking, introducer placement, needle placement

Subgroup levels will only be considered if there are at least 8 subjects within the covariate level across both treatments.

